Malignant tumors are often associated with weakness and cachexia. The clinical characteristic changes of tumor cachexia are continuously skeletal muscle reduction, which can not be corrected by routine dietary supplement, which may cause progressive functional decline and disorder [3]. Sarcopenia is defined as skeletal muscle mass (SMM) combined with skeletal muscle dysfunction. Now it is considered that the occurrence of primary sarcopenia is mainly related to age, and the occurrence of secondary sarcopenia is related to systemic acute and chronic diseases. In recent years, according to the latest definition of the Asian Working Group for Sarcopenia, the definition of sarcopenia has been clarified, the ICD code of the disease has been defined, and a unified diagnosis has formed [4]. Clinical studies on sarcopenia and cancer have also attracted more attention, such as digestive tract tumor, pancreatic cancer, gastric cancer, urologic tumors and rectal cancer [5][6]. Data had show that the prevalence of sarcopenia in lung cancer patients can reach as high as 43%, although sarcopenia is an elderly syndrome closely related to age, clinical rehabilitation or dietitian intervention diet can improve the nutritional status of patients with lung cancer to a certain extent. Although the diagnostic criteria of sarcopenia have been confirmed, most of the research are limited to the toxic and side effects of chemotherapy, postoperative complications and the survival rate of sarcopenia and other malignant tumors. There are few studies that have attempted to

investigate the impact of sarcopenia on the prognosis of lung cancer. Previous studies have also found that nutritional status plays an important role in tumor cachexia of other systems [7]. Loss of appetite, weight loss and fatigue caused by tumor will lead to poor nutritional status or even malnutrition. Poor nutritional status will further reduce patients' appetite and physical activity, thus forming a vicious circle. Nutrition is also an important factor in the progression of sarcopenia disease. Therefore, it is also of great clinical significance to determine whether nutritional status will affect the prognosis of patients with tumor sarcopenia, so it is absolutely valuable to investigate the risk factors associated with sarcopenia in lung cancer patients and confirm the impact of nutritional status on prognosis among these patients.

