1. Identify the prevalence of sarcopenia in patients with early and mid-term non-small cell lung cancer as well as the anthropometry, clinical characteristics, tumor stage and treatment methods of this population, to compare and analyze the differences of clinical characteristics such as smoking status, tumor stage, EGFR gene expression, nutritional score and physical endurance with patients with non-small cell lung cancer.
2. Multivariate logistic analysis aim to explore the related risk factors of sarcopenia in patients with early and mid-term non-small cell lung cancer.
3. To clarify the impact of sarcopenia on the overall survival rate and progression-free survival rate of early and mid-term non-small cell lung cancer, and its clinical value as a predictor of the prognosis of patients.

3、Type of experimental design, grouping method

- 1) Study case collection scope: including respiratory ward, respiratory intensive care unit and respiratory outpatient department of Huadong Hospital Affiliated to Fudan University.
- 2) This study was a prospective, and observational cohort study. The follow-up results were grouped according to the diagnostic criteria of sarcopenia.

4、Case inclusion criteria and exclusion criteria

1. inclusion criteria

- (1) The patients with non-small cell lung cancer diagnosed by cytology or pathology meet the standards of clinical diagnosis and treatment guidelines for lung cancer of Chinese Medical Association (2018 Edition), and the TNM staging diagnosis of lung cancer meets the stage IA-IIIA.

(2) The medical records are complete.

2. exclusion criteria

- (1) Severe heart failure, acute progressive pulmonary inflammation ,acute liver and kidney dysfunction in recent 2 weeks;
- (2) Incomplete clinical and follow-up data or disagreement or inability to conduct regular follow -up CT imaging evaluation;
- (3) Patients with other malignant tumors and a history of related tumor chemotherapy within half year, previous history of radiotherapy;
- (4) Unable to stand or walk, unable to cooperate to complete the walking test, and patients with past unconscious fall history and fall risk;
- (5) Unable to complete BIA examination due to pacemaker implantation and other reasons;
- (6) Those who withdraw from the study for subjective reasons, regardless of the patient's loss of follow-up caused by any reason, shall be regarded as patients who withdraw from the study.

5、 Estimation of case sample size

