Prevalence of lung cancer in China is about 36.09/10 million, with mortality of 28.41/10 million. The prevalence of sarcopenia in Asia is 25.2%. Combined with reported correlation coefficient OR3.2 of tumor and sarcopenia, GPOWER is used to calculate the incomplete information and missing value below 10%. α Less than or equal to 0.05 and statistical inspection force $1 - \beta$ When it is 0.8, it is estimated that the final required numbers for this study includes about 66 patients with lung cancer complicated with sarcopenia. According to the 1:1 ratio of sarcopenia and non sarcopenia, the overall sample size is about 132, so as to ensure that the efficiency of the control test is 80%.

6、 Research process

1. Demographic data

The gender, age, height, weight, body mass index and skeletal muscle mass index were recorded.

2. Clinical data

According to the Electronic Medical Record, system image record data, face-to-face or

telephone follow-up records, clinical data were collected: oral drugs, smoking status (no smoking history, past smoking history, now smoking), tumor stage at the time of diagnosis, other chronic diseases, tumor pathological type and stage. According to the definition of tumor, lymph node and metastasis TNM stage in the eighth edition of American Lung Cancer joint staging. ECOG (Eastern Cooperative Oncology Group performance status, PS), MNA (mini nutritional assessment) nutrition score, quality of life depression score and treatment strategy.

3. Examination data

Serological samples: blood routine, C-reactive protein, blood cholesterol level, albumin level, tumor markers CEA, cyfra211, NSE, SCC, EGFR gene expression.

Imaging examination: chest CT.

4. Diagnostic criteria of sarcopenia

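### Section 5 plans about 66 sarcopenic and 66 non-sarcopenic patients, but nothing in the plan would produce a 1:1 split, and neither sarcopenia prevalence it quotes gives one

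*Combined protocol and SAP*

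**What the plan says.** Section 5 (Estimation of case sample size) starts from a general figure, "The prevalence of sarcopenia in Asia is 25.2" per cent, and an effect size: "Combined with reported correlation coefficient OR3.2 of tumor and sarcopenia". With alpha 0.05, power 0.8 and missing data below 10%, it concludes that "it is estimated that the final required numbers for this study includes about 66 patients with lung cancer complicated with sarcopenia". It then doubles this: "According to the 1:1 ratio of sarcopenia and non sarcopenia, the overall sample size is about 132". The aim given for that total is a power of 80%.

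The other sections describe how patients enter and how groups are formed:

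- Section 2, item 1, gives as a research purpose: "Identify the prevalence of sarcopenia in patients with early and mid-term non-small cell lung cancer".
- Section 3 says: "This study was a prospective, and observational cohort study". Grouping is by the diagnostic criteria for sarcopenia.
- Section 4 admits stage IA-IIIA non-small cell lung cancer. No inclusion or exclusion criterion refers to sarcopenia status.
- Section 8 divides patients by whether sarcopenia was diagnosed.
- Section 10 recruits by clinical case collection from the ward, the intensive care unit and the clinic.

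The introductory background gives the only lung cancer figure: "the prevalence of sarcopenia in lung cancer patients can reach as high as 43" per cent. No section mentions a quota, matching or stratified enrolment, and no prevalence is given for stage IA-IIIA disease.

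**The concern.** When patients are not chosen on the grouping factor, the group ratio is a result of the study and not a design setting. Here the grouping factor is also the quantity that the first research purpose sets out to estimate, so a planned 1:1 split presupposes that answer at about 50%. The plan quotes two prevalences and neither is near 50%.

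Two things are at stake. First, the number of sarcopenic patients that section 5 calls for may not be reached with the enrolment described. Second, staff reading section 5 cannot tell whether to enrol every eligible patient or to balance the groups. If they balance informally, the enrolled proportion is pulled towards 50% and no longer estimates prevalence, and a reader of the results could not detect this.

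**Working it through.** **Inputs.** Sarcopenia prevalence 25.2% (Asia, section 5) and at most 43% (lung cancer, background). Odds ratio 3.2, alpha 0.05, power 80%, missing data below 10%, about 66 sarcopenic patients, N about 132 (all section 5). Assumed, because the plan does not say: a two-sided test and a 10% loss.

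**1. Where 66 comes from.** Apply the odds ratio to the Asian figure:

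- Odds = (0.252 / 0.748) × 3.2 = 1.078, so p = 1.078 / 2.078 = 0.519.

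Size a two-sided comparison of 25.2% with 51.9% (difference 0.267, mean 0.385):

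- n = [1.96 × √(2 × 0.385 × 0.615) + 0.842 × √(0.252 × 0.748 + 0.519 × 0.481)]² / 0.267² = about 51.0, so 52 per group.
- With the continuity correction, n' = (n/4) × [1 + √(1 + 4/(n × 0.267))]² with n = 51.0 gives 58.3, so 59 per group.
- Allowing for 10% loss, 59 / 0.9 = 65.6, so 66 per group and 132 in total.

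This matches the plan exactly. Fisher's exact test also needs 59 per group. The other variants tried do not match after inflation: 58 without the correction, 54 with unpooled variance, and 46 or 54 one-sided. In the matching calculation sarcopenia is the outcome and the groups are a reference population and tumour patients. On this reconstruction 66 is a group size and not a count of sarcopenic patients.

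**2. Sarcopenic patients expected among 132, enrolled whatever their status.** Expected count = 132 × p. The chance of at least 66 is a binomial tail.

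| Prevalence | Expected | Expected split | Chance of at least 66 | Enrolment for an expected 66 (66/p) |
|---|---|---|---|---|
| 25.2% | 33.3 | 33/99 | 8 × 10⁻¹⁰ | 262 |
| 43% | 56.8 | 57/75 | 6% | 154 |
| 51.9% (derived, not stated) | 68.5 | 68/64 | 70% | 128 |

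**3. Cost of imbalance.** For a two-group comparison with similar variance in each group, information relative to 66/66 is (1/66 + 1/66) / (1/a + 1/b):

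- 33/99: 0.750, equivalent to 132 × 0.750 = 99 patients split 1:1.
- 57/75: 0.981, equivalent to about 130.
- 68/64: 0.999, equivalent to about 132.

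These ratios need no outcome rate and say nothing about power for progression-free survival.

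**4. Precision of the prevalence estimate at n = 132.** Half-width of the 95% interval = 1.96 × √(p(1 − p)/132): 7.4 points at 25.2%, 8.4 at 43% and 8.5 at 51.9%.

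**5. The quota reading.** If 66 of each were enrolled by design, the sample proportion would be 66/132 = 50% whatever the true prevalence. An estimate would then need the number of patients screened, and the plan describes no screening log.

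**The case against.** The strongest reply is that section 5 does not apply 25.2% to lung cancer patients. It combines that figure with an odds ratio of 3.2, and the two together imply 51.9%, or about 68 of 132. On that reading unselected enrolment gives roughly 1:1, with a 70% chance of at least 66. This stands in part. A reader might infer that the plan must fail whichever way it is read, and the documents do not support that. What remains is that 51.9% is never stated, has no stated basis, and exceeds the plan's own upper figure for lung cancer.

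Three further points also have weight:

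- The plan says about 66 and about 132, so at least 66 is a stricter threshold than the text sets. Expected shortfalls of 9 (66 − 57) or 33 (66 − 33) patients still matter.
- The 25.2% figure is for Asia in general, so 33 is a low-end scenario and not a forecast. At 43% the loss of information is about 2%. It would be wrong to infer a large loss of power in general.
- A quota would not make the first research purpose unreachable. Every candidate would have to be measured before classification, so a screening denominator could be kept. The plan does not provide for one.

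Finally, that the cohort is unselected is inferred from the absence of any criterion or quota. The plan does not say that enrolment is consecutive. That is a reason to state the method, not a defence of the 1:1 split.

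**Conclusion.** The concern holds in this form: the 1:1 split in section 5 has no mechanism in the plan and no stated prevalence behind it. If enrolment ignores sarcopenia status, 132 patients would be expected to include about 57 sarcopenic patients at 43% and about 33 at 25.2%. Only the unstated 51.9% gives about 68. The loss of information is about 2% at 43% and about 25% at 25.2%, assuming similar variance in the two groups. If 1:1 is a quota, the enrolled sample cannot estimate prevalence.

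A reader might also infer that the 80% is a sound equal-group power for sarcopenic versus non-sarcopenic patients, reduced only by imbalance. The documents do not establish this. The 66 per group reproduces as the size for comparing a sarcopenia prevalence of 25.2% with 51.9%, which is a different comparison. That is a reconstruction, since the plan does not name the test, but it is enough to require the sponsor to say what the 80% refers to.

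The total of 132 is not itself an arithmetic error. The statement of the split should be corrected.

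**What to change.** In sections 5 and 10:

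1. State that eligible patients are enrolled regardless of sarcopenia status.
2. Replace 66/66 with the expected split for N = 132: about 57/75 at 43%, with 33/99 at 25.2% as a low-end case. If 51.9% was assumed, give 68/64 and state that prevalence and its basis.
3. Add the expected precision of the prevalence estimate: a 95% interval half-width of about 7 to 9 points.
4. State which comparison the 80% refers to. Do not present it as power for sarcopenic versus non-sarcopenic patients at the expected split unless it is recalculated for that comparison.
5. If a quota is intended, say so, keep a log of screened patients, and estimate prevalence from that log only.

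The cost is wording, plus a recalculation if the 80% is to be kept for the two-group comparison, and a screening log if a quota is kept. No extra patients are needed, provided the target of about 66 sarcopenic patients is given up. The downside is that the stated number of sarcopenic patients becomes less favourable. Keeping an expected 66 without a quota would need about 154 (at 43%) to 262 (at 25.2%) enrolled, which is not proposed here.

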The diagnosis process of sarcopenia complies with the provisions of the Asian sarcopenia working group. The specific information collected for diagnosis includes: skeletal muscle mass of limbs: the skeletal muscle mass index (ASMI) is measured by Korea inbody570 (Korea Biospace) human composition analyzer. The decrease of skeletal muscle mass is defined as the decrease of male $< 7.0\text{kg}/\text{m}^2$ and female $< 5.7\text{kg}/\text{m}^2$; The Jamar hand dynamometer (USA) is used to measure the grip strength in the grip strength test. Patients are required to hold the grip strength tester in the dominant hand with standing position for 3 times, the maximum value were recorded. Male $< 28\text{kg}$ and female $< 18\text{kg}$ are defined as reduced grip strength; The time required for patients to walk at normal pace was measured by 6-meter distance pace measurement; If the walking speed is less than $0.8\text{m}/\text{s}$, it is defined as the decline of walking function; The decrease of ASMI accompanied by the decrease of grip strength or gait speed was diagnosed as sarcopenia.

5. Follow up endpoint

The primary endpoint was progression free survival (PFS) within 2 years, defined as the time from diagnosis to clinically recorded disease progression or death from any cause. The patients were followed up according to the outpatient and electronic medical records and telephone calls. The tumor treatment strategy and the time of clinical outcome or disease progression were followed up. The disease progression was defined as the 20% increase in sum of longest diameters from nadir (and a minimum absolute increase of 5 mm), or unequivocal increase in nontarget lesions according to RECIST solid tumor standard. The progress needs to be confirmed by at least one imaging and one clinical expert. The deadline for follow-up is 2 years. The secondary endpoint was overall survival time (OS), defined as

the outcome of patient death from diagnosis to any cause or the final follow-up time. During the follow-up, the researchers conducted disease evaluation, follow up of disease progress, grip strength test, walking test, muscle density measurement and nutritional score (MNA) at 6, 12, 18 and 24 months after enrollment. If feasible, the participants will continue to be followed up for up to five years.

7、Adverse events

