2. Analysis of risk factors of non-small cell lung cancer combined with sarcopenia: univariate and multivariate logistic analysis of relevant variables of patients with sarcopenia, including clinical data variables, nutritional status, tumor stage, serum C-reactive protein, cholesterol level, albumin level, EGFR gene expression, etc, Logistic regression was used to analyze the risk factors of sarcopenia in non-small cell lung cancer.
3. Prognostic value of sarcopenia in non-small cell lung cancer: progression free survival time PFS and overall survival time OS were statistically analyzed by Kaplan-Meier, and the difference was tested by log-rank method.

9、 Ethics related to experiment

The risk of patients participating in this study comes from the risk of tumor itself and tumor complications. It is an observational study without any intervention means such as drugs. The study itself does not increase the disease risk of patients. Patients can still stop treatment or withdraw from the study at any time, and subjects can stop the study at any time or for any reason at their own request or at the request of the investigator. For all subjects who withdrew from the study for any reason, contact themselves or their families or health care providers 24 weeks after withdrawal to determine the subject's life status. Subjects may voluntarily stop participating in the study at any time without affecting further treatment.

At the same time, ensure that after the end of the study and midway suspension, all participants continue to accept the disease medical measures recommended in the guidelines, do not change the follow-up further treatment, and do not intervene in the outcome of the disease.

10、 Recruitment methods and informed consent of subjects

This study used the recruitment method of clinical case collection, including respiratory ward, respiratory intensive care unit and respiratory clinic. All patients must

obtain informed consent and sign the informed consent form.

11、Expected progress and completion time of the study

Study period: October 15, 2021 to October 15, 2024

From October 2021 to November 2021, the research group collected personnel training and enrolled cases.

From November 2021 to November 2023, the case observation indexes, clinical data and follow-up data were collected.

From November 2023 to January 2024, the final follow-up was completed and the outcome events were collected and sorted out.

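### PFS and OS are timed from diagnosis but patients are observed only from enrolment, with no limit on the gap, no progression-free entry rule and no delayed entry in the analysis

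*Combined protocol and SAP*

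**What the plan says.** Section 6, item 5 of the combined protocol and SAP makes PFS within two years the primary endpoint, "defined as the time from diagnosis to clinically recorded disease progression or death from any cause". OS, the secondary endpoint, is "the outcome of patient death from diagnosis to any cause or the final follow-up time". The same item schedules assessments "at 6, 12, 18 and 24 months after enrollment" and adds: "The deadline for follow-up is 2 years". That last sentence names no starting point.

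Section 10 requires every patient to "obtain informed consent and sign the informed consent form", so a patient must be alive to enter. Recruitment is from the respiratory ward, intensive care unit and clinic. Section 4 asks for cytologically or pathologically diagnosed stage IA-IIIA disease and complete records. It does not ask for newly diagnosed disease, a maximum time since diagnosis or freedom from progression. Section 6, item 2 records stage as it was at diagnosis.

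Section 8, item 3 says that PFS and OS "were statistically analyzed by Kaplan-Meier, and the difference was tested by log-rank method". No section mentions delayed entry, left truncation, a landmark or enrolment as time zero. The date of the baseline sarcopenia assessment is not stated; that it falls at enrolment is an inference.

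**The concern.** The endpoint clock and the observation clock start at different points. If a patient is diagnosed in month 0 and consents in month 6, death in the first six months was impossible for that patient as a cohort member. A Kaplan-Meier curve from diagnosis nevertheless counts those months as time at risk. This is immortal time for OS and for the death component of PFS. It is immortal for all of PFS if already progressed patients are kept out. If they are let in, they arrive with the primary event behind them, and the plan has no rule for them.

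There is also a plain mismatch of horizons. With a six-month lag, the 24-month visit takes place 30 months after diagnosis, and the 18-month visit is the last inside a two-year window from diagnosis.

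At stake are the reported two-year rates and, if lags differ between the sarcopenia groups, the comparison behind the third research purpose in section 2.

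**Working it through.** **The plan's own figure.** Section 5 gives 66 per group. It reproduces: 25.2% with an OR of 3.2 implies 51.9%; a two-sided 5% test with continuity correction and 80% power needs 59 per group; 59/0.9 = 65.6, rounded up to 66, or 132 in total. This is a comparison of proportions. It uses no time origin and does not bear on the point.

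**Inputs.** The documents give no lag, event rate or hazard ratio. Assumed: constant hazard h = -ln(S)/2 per year; diagnosis-to-enrolment lag uniform on 0 to m years, with m = 0.25, 0.5 or 1; true two-year OS 90%; true two-year PFS 70% against 49%, which is HR 2.0.

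**Step 1: OS, where death blocks entry.** Apparent S(2) = S(2)/A, where A = [1 - exp(-hm)]/(hm) is the chance of reaching enrolment. For S = 0.90, h = 0.0527 and A = 0.9934, 0.9869, 0.9741. Apparent OS is 90.6%, 91.2% and 92.4%.

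**Step 2: PFS of 70%, by who enters.** Here h = 0.1783 and A = 0.978, 0.957, 0.916.
- Only deaths block entry, with deaths a share d of first events and progressed patients surviving to enrolment: apparent S = 0.70/[1 - d(1 - A)]. For d from 10% to 50% this is 70.2-70.8% (lags 0-3 months) and 70.6-73.1% (lags 0-12 months).
- Every earlier event blocks entry: 0.70/A = 71.6%, 73.2% and 76.4%.
- Progressed patients are r times as likely to be enrolled: apparent S = 0.70/[A + r(1 - d)(1 - A)]. With m = 1, d = 10% and r = 2, this is 0.70/(0.916 + 2 x 0.0757) = 65.6%, below the truth. The bias is zero at r = 1/(1 - 0.10) = 1.11.

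**Step 3: hazard ratio with diagnosis as origin and no delayed entry (simulation).**

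| Lags, sarcopenic vs others | What blocks entry | True 2.0 appears as | True 1.0 appears as |
|---|---|---|---|
| Equal | all events | about 2.0 | about 1.0 |
| 0-6 vs 0-3 months | all events | about 1.85 | 0.93 |
| 0-12 vs 0-3 months | all events | about 1.6 | about 0.78 |
| 0-3 vs 0-12 months | all events | about 2.6 | about 1.29 |
| 0-12 vs 0-3 months | deaths only | 1.80-1.97 | 0.90-0.98 |
| 0-3 vs 0-12 months | deaths only | 2.04-2.23 | 1.02-1.12 |

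At 66 per group with all events blocking, a nominal 5% test of a true HR of 1.0 rejects in about 5% of runs with equal lags, 5-6% with 0-6 vs 0-3 months and about 10-12% with 0-12 vs 0-3 months.

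**Step 4: events inside two years of diagnosis, all events blocking.** With no lag, 66 x (0.300 + 0.510) = 53.5. With lags, apparent PFS in the worse group is 51.2%, 53.5% and 58.3%, so expected events fall to 51.0, 48.4 and 43.1. Power for HR 2.0, as Φ(√(D/4) x ln 2 - 1.96) with D events, goes from 72% to 70%, 67% and 62%. The 72% itself is a sample-size matter, not part of this point.

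**The case against.** The strongest reply is that the harm is conditional. If everyone is enrolled at diagnosis, the bias vanishes. The planned test is a comparison between groups, and equal lags leave it nearly intact. Only a strong assumed contrast in lags doubles the false-positive rate, and nothing in the documents supports that contrast or its direction. This stands, and it limits the conclusion.

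A reader might infer that any lag overstates PFS. The documents do not support that. Section 4 does not bar progressed patients, and recruitment from ward and clinic could over-sample them. Step 2 shows that mild over-sampling cancels the bias and twofold over-sampling reverses it. The statement holds for OS only.

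A reader might also infer that the sarcopenia comparison is biased as planned. That needs lags that differ by sarcopenia status, which the documents neither show nor exclude.

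One may argue that the two-year horizon simply means two years of follow-up. The calendar in section 11 gives some support: "From October 2021 to November 2021, the research group collected personnel training and enrolled cases", with final follow-up from November 2023 to January 2024. If that line is the enrolment window, the schedule fits a count from enrolment. But the endpoint still starts at diagnosis, so the two remain to be reconciled. Records, telephone calls and optional follow-up to five years help to capture late events, but they do not settle the origin.

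Exclusion (3) in section 4, on chemotherapy within half a year and previous radiotherapy, may shorten some gaps. It sets no limit, and its wording may concern other tumours only.

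**Conclusion.** The point holds in this form. The plan times both survival endpoints from diagnosis, observes patients from enrolment, and has neither an entry rule nor an analysis that allows for the difference.

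- OS from diagnosis is overstated with any lag: by 0.6 to 2.4 points for a true 90%.
- PFS from diagnosis has a bias of unknown direction. A true 70% appears as 70.2-73.1% if only deaths block entry, 71.6-76.4% if every earlier event does, and about 66% in the twofold over-sampling example.
- The group comparison is close to unbiased with equal lags and materially biased only with clearly unequal ones.
- With any lag, the 24-month visit lies outside a two-year window from diagnosis. This needs no assumption about bias.

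Every size rests on assumed lags, rates and constant hazard. The real lag could be negligible; the plan does not ask for it to be reported by group, so readers could not tell.

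**What to change.** In section 6, item 5 and section 8:

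- Make the baseline sarcopenia assessment, done at enrolment, time zero for group assignment, Kaplan-Meier curves and the two-year horizon. This matches the visit schedule.
- Label the results as PFS and OS from baseline. Under Weibull hazards with shapes 0.6 to 1.6 and lags of 0-12 months, a PFS of 70% from diagnosis corresponds to 77.0% down to 62.9% from baseline, so the two are not interchangeable.
- Restrict PFS to patients with no recorded progression by baseline.
- Record the diagnosis, enrolment and baseline dates, and report the diagnosis-to-baseline lag by group.
- Compare groups with a Cox model on the time scale since diagnosis, with delayed entry at baseline and follow-up to two years after baseline. If the software (SPSS 24.0) cannot fit it, use a Cox model from baseline adjusted for time since diagnosis.

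An unadjusted comparison from baseline is not enough if lags differ: under the same Weibull shapes with lags of 0-12 vs 0-3 months in either direction, a true HR of 1.0 came out at 0.83-1.22, against 0.98-1.01 with delayed entry and 0.96-1.03 with lag adjustment.

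The cost is a few sentences, one model and one date not already implied by the plan; no visits are added. Results become less comparable with PFS from diagnosis, and patients who progressed before baseline are lost from PFS. At 66 per group, a true HR of 2.0 and lags of 0-12 vs 0-3 months in either direction, power is 63-67% with delayed entry but 40-53% with the lag-adjusted fallback. With equal lags the fallback costs almost nothing (70-71%).

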1. During the walking test, trained doctors and nurses were trained to detect the exercise safety in the whole process. This study will practically implement the safety work and safety equipment in the implementation of the scheme, including oxygen inhalation, oximeter, defibrillator, cardiopulmonary resuscitation drugs, bronchodilators and nitroglycerin; In case of the following conditions, the test will be terminated strictly: 1. Reaching 85% of the maximum heart rate; 2. Arrhythmia events; 3. Blood pressure exceeding 180 / 100mmhg; 4. Chest pain; 5. Blurred vision; 6. Cold sweat syncope; 7. Abnormal limb coordination; 8. Blood oxygen saturation lower than 85%.
2. This study is an observational study and does not involve new drugs and traumatic testing, so there is basically no additional research risk. In case of acute exacerbation or condition change during the study, the patient may not be affected by the study and be treated in accordance with the medical principles. The end point of observation and disease progress indicators are the objective state of the development of the disease itself. The study does not involve any research methods and drugs for intervention and diagnosis measures, so there will be no serious adverse events related to the study.

8、Statistical analysis

The patients were divided into two groups according to whether they were diagnosed as sarcopenia, and the differences of clinical data between the two groups were analyzed. The statistical analysis will be calculated by spss24.0 statistical analysis software.

1. Demographic characteristics and clinical data analysis: describe the age and gender distribution of patients, group patients according to whether they are diagnosed as sarcopenia, and analyze the differences of clinical data such as age distribution, smoking, tumor type and clinical stage between the two groups. Continuous variables are represented by mean standard deviation, classified variables are represented by

percentage, students t-test analysis and Mann-Whitney U test are used according to data type differences, and chi square test is used for component comparison of classified data.

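### Does the PFS definition fail to count new lesions, or recurrence in a patient with no lesion left?

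*Combined protocol and SAP*

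**What the plan says.** Section 6, item 5 (Follow up endpoint) holds the only progression rule in the combined protocol and SAP. PFS is "defined as the time from diagnosis to clinically recorded disease progression or death from any cause", taken over two years. Progression then has two routes. One is measured: "The disease progression was defined as the 20% increase in sum of longest diameters from nadir (and a minimum absolute increase of 5 mm". The other is a judgement: "unequivocal increase in nontarget lesions according to RECIST solid tumor standard". No version of the standard is named. A confirmation step follows: "The progress needs to be confirmed by at least one imaging and one clinical expert". Disease is evaluated alongside "muscle density measurement and nutritional score (MNA) at 6, 12, 18 and 24 months after enrollment".

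Section 4 requires that "the TNM staging diagnosis of lung cancer meets the stage IA-IIIA". Treatment is recorded under section 6, item 2, but not restricted. Section 8, item 3 gives the analysis: "progression free survival time PFS and overall survival time OS were statistically analyzed by Kaplan-Meier, and the difference was tested by log-rank method". No section uses the terms new lesion, recurrence or relapse for an event, and none gives a rule for a patient with no lesion left to measure.

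**The concern.** On their ordinary meaning, both routes describe growth of disease already present. Two kinds of patient do not fit easily. In the first, disease appears at a new site while the known lesions are stable. In the second, treatment has left no visible tumour, so the sum of diameters is zero or does not exist and a 20% rise has no content. Since stages IA to IIIA are eligible and surgery is not excluded, the second kind can be enrolled.

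The log-rank test uses both whether and when an event occurred. If the two routes were treated as a closed list, some recurrences would be counted late, only at death, or not at all. If assessors differed in their reading, PFS would depend partly on who did the scoring. Because this is the primary endpoint, the point deserves a check.

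**Working it through.** **1. The measured route in a lesion-free patient.** The rise needed is the larger of 5 mm and 20% of the nadir sum.

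- Nadir 30 mm: 20% is 6 mm, so the threshold is 6 mm.
- Nadir 0 mm: 20% is 0 mm, so the threshold is 5 mm.

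Regrowth of at least 5 mm at a measured site is therefore arguably covered as written. A new lesion outside the measured set adds 0 mm to the sum and does not meet this route.

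**2. The judgement route.** An increase in nontarget lesions can mean size or number. Even on the size-only reading, a lesion first seen at one visit can be followed as nontarget and counted when it clearly grows. A lesion seen at 6 months and scored at 12 is an event 12 − 6 = 6 months late; it is not a lost event.

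**3. Longest possible misdating.** Suppose the recurrence is never scored and the patient is alive and censored at the 24-month visit. The time wrongly counted as progression-free is 24 − 6 = 18, 24 − 12 = 12 or 24 − 18 = 6 months, for detection at 6, 12 or 18 months. These are upper limits. They assume no later qualifying growth. They also assume that the window closes at the 24-month visit, although visits run from enrolment and PFS from diagnosis. If the two-year window also runs from diagnosis, a patient enrolled after diagnosis leaves it sooner and the figures shrink.

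**4. Effect per patient.** With 66 per group (section 5), one uncounted recurrence lowers the crude event proportion by 1/66 = 1.5 percentage points, three by 3/66 = 4.5 and five by 5/66 = 7.6. That holds for any miscoded event and says nothing about how many there would be.

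**5. Total effect.** Let s be the share of true events that are recurrences of this kind, and f the fraction of those still counted, through later growth, death or a broad reading of the rule. The share of events kept is 1 − s(1 − f). The documents give neither quantity. Assuming s = 0.1, the result runs from 0.90 (f = 0) to 1.00 (f = 1). Assuming s = 0.3, it runs from 0.70 to 1.00. The range includes no loss at all, and nothing in the plan narrows it from below.

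**6. Link to the sample size.** Section 5 gives 66 per group. From prevalence 0.252 and odds ratio 3.2, the odds are 3.2 × 0.252/0.748 = 1.078, so the second proportion is 1.078/2.078 = 0.519. A two-sided 5% comparison of two proportions at 80% power with continuity correction needs 59 per group, and 59/0.9 = 65.6, rounded up to 66, or 132 in total. That reproduces the stated figure. It uses no PFS event rate, so the progression rule has no bearing on it.

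**The case for a change.** The strongest opposing case is that a primary endpoint should not rest on inference. The text spells out two routes and stops, names no version of the standard, and gives the experts a confirmation step without the rule they are to confirm. One or two added sentences would close the gap, with no extra visits or scans.

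The factual part stands: the rule for new lesions and for lesion-free patients is not written out. What the cited standard says about new lesions cannot be read from these documents either, so the citation alone does not settle the matter.

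The consequence does not follow, however. The plan never says that the two routes are the only ones. The event is defined as progression in the clinical record, and both an imaging and a clinical view must support it. It is hard to see both supporting the view that disease has newly appeared and still recording the patient as progression-free. The statement in section 7 that "The end point of observation and disease progress indicators are the objective state of the development of the disease itself" does not strengthen the case: it argues that an observational study adds no risk, and makes no claim about agreement between assessors.

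**Conclusion.** No change to the plan is called for. The wording is incomplete, but competent assessors would fill the gap in the obvious way, scoring an unequivocal new lesion, or the first documented recurrence in a lesion-free patient, as progression on the date it is documented. On that reading no event is lost or delayed.

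The conclusion rests on two points of reading: that the two routes summarise the cited standard and are not a closed list, and that the clinical-record wording and the two-part confirmation govern how a case is scored. If assessors instead applied the routes literally, each recurrence never counted would cost 1.5 percentage points in its group's crude event proportion, and the misdating would be at most 18 months. The number of such cases cannot be derived from the plan. The same wording applies to both sarcopenia groups, and no bias between them has been shown. The planned Kaplan-Meier and log-rank analysis and the sample size of 132 are unaffected.
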